**Table 6. Medications Contraindicated for Use with the Study Drug Regimen**

For medications contraindicated with AbbVie's 3 DAA regimen, refer to the recommended prescribing information section of the approved local product labels in countries where the regimen contained in this study (i.e., ABT-450/r/ABT-267 and ABT-333) has received marketing authorization. If locally approved labels are not available, refer to the following Contraindicated Medication list:

Alfuzosin	Ethinyl estradiol-containing medications	Pimozide
Astemizole	Fusidic Acid	Rifampin
Carbamazepine	Gemfibrozil	Salmeterol
Cisparide	Lovastatin	Sildenafil*
Dihydroergotamine	Methylergonovine	Simvastatin
Efavirenz	Midazolam (oral)	St. John's Wort
Ergotamine	Phenobarbital	Terfenadine
Ergonovine	Phenytoin	Triazolam

\* When used for the treatment of pulmonary arterial hypertension.

Note: Not all medications contraindicated with ritonavir, ribavirin, and 3DAA regimen are listed above. Refer to the most current package inserts or product labeling of ritonavir and ribavirin for a complete list of contraindicated medications.

4. Use of known moderate or strong inducers of cytochrome P450 3A (CYP3A) or strong inducers of cytochrome P450 2C8 (CYP2C8) or strong inhibitors of CYP2C8 within 2 weeks of the respective medication/supplement, prior to initial dose of study drug.
5. Clinically significant abnormalities or co-morbidities, other than HCV infection that in the opinion of the investigator make the subject an unsuitable candidate for this study or drug regimen.
6. Current enrollment in another interventional clinical study, previous enrollment in this study, prior or current use of any investigational or commercially available anti-HCV agents other than IFNs or RBV (including previous exposure to ABT-450, ABT-267 or ABT-333), or receipt of any investigational product within 6 weeks prior to study drug administration.
7. History of solid organ transplant.
8. Screening laboratory analyses showing any of the following abnormal laboratory results:
  - Creatinine Clearance (CrCl) < 30 mL/min as estimated by the Cockcroft-Gault equation:
$$\text{CrCl} = \frac{[(140 - \text{Age}) \times \text{Mass (in kg)} \times (0.85 \text{ if female})]}{[72 \times \text{Serum creatinine (in mg/dL)}]}$$
  - Albumin < 2.8 g/dL
  - Hemoglobin < LLN
  - Platelets < 25,000 cells per mm^3
  - Total bilirubin > 3.0 mg/dL

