9. Any current or past clinical evidence of Child-Pugh B or C Classification (Child-Pugh Score  $\geq$  7) or clinical history of liver decompensation such as ascites (e.g., as noted on a physical exam or imaging test), variceal bleeding or hepatic encephalopathy.

10. Confirmed presence of hepatocellular carcinoma indicated on imaging techniques such as computed tomography (CT) scan or magnetic resonance imaging (MRI) within 3 months prior to Screening or on an ultrasound performed at Screening (a positive ultrasound result will be confirmed with CT scan or MRI.)
11. HCV genotype performed during screening indicating infection with any genotype other than genotype 1.

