#### **8.1.2.1 Primary Efficacy Endpoint**

The primary efficacy endpoint is to assess the effect of response to treatment on clinical outcomes by comparing the time to incidence of the following events between subjects who achieve SVR12 and those who do not using a Cox regression model:

- All-cause death
- Liver-related death
- Liver decompensation
- Liver transplantation
- Hepatocellular carcinoma
- Composite of any of the above outcomes

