7.1 Demographic and Baseline Characteristics

Demographics include age, weight, height and BMI as continuous variables, and sex, race, ethnicity, age category (< 55 years or ≥ 55 years] and [< 65 or ≥ 65 years]), birth year (< 1945 , 1945 to 1965, > 1965), country, and BMI category (< 30 kg/m² or ≥ 30 kg/m²).

Baseline characteristics will include: HCV genotype 1 subtype (1a, 1b, 1-other), IL28B genotype ([CC, CT, or TT] and [CC or non CC]), prior treatment history (treatment-naïve [IFN-eligible, IFN-ineligible] or IFN-based treatment-experienced [null responder, partial responder, relapser, prior relapse/breakthrough, prior nonresponder, IFN-intolerant and IFN experienced-other]), baseline HCV RNA levels ([continuous (use log₁₀ HCV RNA)])

and [$< 800,000$ IU/mL or $\geq 800,000$ IU/mL]), baseline HOMA-IR (< 3 or ≥ 3 $\text{mU} \times \text{mmol/L}^2$), baseline fibrosis stage (F0 – F1, F2, F3, F4), baseline Child-Pugh score (non-cirrhotic, 5, 6, or > 6), baseline FibroTest score (continuous and [< 0.49 , $0.49 - 0.58$, $0.59 - 0.74$, ≥ 0.75]), baseline albumin (continuous), baseline albumin (< 35 , ≥ 35 g/L), baseline creatinine clearance (continuous; < 30 mL/min, $\geq 30 - 49$ mL/min, $\geq 50 - 89$ mL/min, ≥ 90 mL/min), baseline eGFR by MDRD (continuous; < 30 , $30 - 59$, $60 - 89$, ≥ 90 mL/min/1.73 m²; < 60 or ≥ 60 mL/min/1.73 m²), baseline platelet count (continuous; $< 90 \times 10^9/\text{L}$, $\geq 90 \times 10^9/\text{L}$; $< 50 \times 10^9/\text{L}$, $\geq 50 \times 10^9/\text{L}$; $< 100 \times 10^9/\text{L}$, $\geq 100 \times 10^9/\text{L}$; $< 150 \times 10^9/\text{L}$, $\geq 150 \times 10^9/\text{L}$), baseline alpha fetoprotein (continuous, and < 20 ng/mL, ≥ 20 ng/mL), tobacco (user, ex-user, or non-user) and alcohol (drinker, ex-drinker, or non-drinker) use status, history of diabetes, history of depression or bipolar disorder, history of bleeding disorders, AST to platelet ratio index (APRI) (continuous; ≤ 2.0 or > 2.0), and Fibrosis-4 score (FIB-4) (continuous; ≤ 3.25 , > 3.25).

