For each of the six event types, a test statistic based on Kaplan-Meier estimates of the event-free survival probability at Year 5 and the estimated variance will be constructed to test the null hypothesis that the 5-year event-free survival rates for subjects who have achieved SVR₁₂ and those who haven't are the same.

For each of the six event types, a Cox proportional hazards (PH) model will be constructed to include all the baseline characteristics as described in Section 7.1, SVR₁₂ status, and other variables as appropriate to compare the risk of experiencing a clinical outcome between subjects who have achieved SVR₁₂ and those who haven't.

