The 2-sided 95% Wilson score confidence interval for a binomial proportion (percentage of subjects achieving SVR₁₂) will be produced for each subgroup with at least 10 subjects. In addition, stepwise logistic regression will be performed on both SVR₁₂ and virologic failure (on-treatment virologic failure or relapse) using subgroup variables as described above. Some variables may be treated as continuous to decrease the chance of separation or quasi-separation and some variables may be eliminated if missing for too many subjects.

For GT1 non-b subjects with cirrhosis only:

- Treatment Duration (12 weeks, 24 weeks);

The analysis on liver stiffness (change and percentage change from baseline in FibroScan score) as described in Section 10.4 will be performed on the mITT-I-GT population for the following subgroup (assessed at baseline), as appropriate:

- The presence of cirrhosis (subjects with cirrhosis vs subjects without cirrhosis);

Subgroup analyses will be performed if there are an adequate number of subjects.

The effect of subgroup status on change and percentage change from baseline in FibroScan score (assessed at the end of treatment and all post-treatment visits except PT Week 4) will be evaluated if there are at least 10 subjects in each subgroup using summary statistics and ANOVA analyses separately for each applicable visit. The subgroup status, SVR₁₂ status, and their interaction will be included in the model. From the ANOVA analyses, point estimates of the mean difference from the reference subgroup (subjects without cirrhosis) and 95% confidence intervals will be provided.

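### SAP 10.3 enters every Section 7.1 baseline characteristic in six Cox models with no coding or sparse-event rule: a small cost for the composite, a real one for rare components, while the log-rank test ignores cirrhosis

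*SAP*

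**What the plan says.** Protocol 8.1.2.1 compares time to event between subjects who achieve SVR12 and "those who do not using a Cox regression model"; it names no covariates. SAP 10.3 supplies them. For each of six event types the Cox "model will be constructed to include all the baseline characteristics as described in Section 7.1", together with SVR12 status "and other variables as appropriate to compare the risk of experiencing a clinical outcome". The same section also compares the two groups by a log-rank test and by a test of Year-5 Kaplan-Meier estimates, with no strata for either. SAP 4.3 bases power on the two-sample log-rank test.

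SAP 7.1 was written for summary tables and gives several characteristics in more than one form, for example "IL28B genotype ([CC, CT, or TT] and [CC or non CC". It also lists "baseline Child-Pugh score (non-cirrhotic, 5, 6, or > 6" and a creatinine clearance class below 30 mL/min. Protocol 5.2.2 excludes "Any current or past clinical evidence of Child-Pugh B or C Classification" (score 7 or more) and "Creatinine Clearance (CrCl) < 30 mL/min as estimated by the Cockcroft-Gault equation".

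SAP 10.5 lets variables be treated as continuous to limit separation, and adds that "some variables may be eliminated if missing for too many subjects". Both allowances apply to the logistic regressions on SVR12 and virologic failure, not to the Cox models. SAP 6.3 bars imputation in efficacy analyses apart from PRO, HCV RNA and resistance-persistence data.

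**The concern.** SVR12 status is an outcome of treatment, not a randomised group, so the adjusted hazard ratio carries the primary conclusion. Four things are unsettled in how it is obtained.

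- **Coding.** Where several forms are listed, the SAP does not say which one enters, so the choice would be made after the data are in.
- **Sparse events.** The same long list is applied to components such as transplantation or liver-related death, which may have few events.
- **Missing covariates.** With imputation barred, the default is a complete-case fit. AFP is measured only at Screening (Protocol Table 8, footnote b) and was added by this amendment (Protocol 1.1), so subjects screened earlier may have no value and would drop out of every model.
- **Unadjusted tests.** Protocol 3.0 says that the risk of complications is highest in advanced fibrosis, and its figures for Study M13-099 show lower SVR12 in cirrhosis. A two-group test without strata therefore leans towards SVR12.

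**Working it through.** **1. The plan's own figure.** Inputs from SAP 4.3: N = 2000, 4% non-SVR12, 20% five-year risk without SVR12, HR 0.25, 20% dropout. Exponential hazards: event 0.0446 per year (non-SVR12) and 0.0112 (SVR12), dropout 0.0446.

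- Non-SVR12: 80 × 0.5 × (1 − 0.8²) = 80 × 0.18 = 14.4 events.
- SVR12: 1920 × 0.2 × (1 − 0.8^1.25) = 1920 × 0.0487 = 93.5 events.
- Total 107.9. Schoenfeld power is 0.806, and simulated log-rank power is 0.97. The stated power above 80% is reproduced.

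**2. Parameters.** Twenty characteristics, demographics not counted. Child-Pugh is scored only in F4 (SAP 7.1), so its non-cirrhotic level duplicates fibrosis stage and one parameter is removed. In listed order, coarsest coding: 2+1+1+1+1+3+2+1+1+1+1+1+1+2+2+1+1+1+1+1 = 26. Three-level IL28B (+1) and nine-level treatment history (+7) give 34. Four-level FibroTest, creatinine clearance and eGFR (+2 each) give 40. SVR12 adds one.

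**3. Events per parameter.** 107.9/27 = 4.0 and 107.9/41 = 2.6. At the planned 2250 subjects: 121.4/27 = 4.5 and 121.4/41 = 3.0.

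**4. Coding freedom.** Nine characteristics have two forms, eGFR three and platelets five: 2⁹ × 3 × 5 = 7,680 one-form-each models. Over 40 random codings per simulated trial, the median ratio of largest to smallest SVR12 HR was 1.24 at 108 events and 1.42 at 40. The 0.05 verdict differed between codings in 2% of trials (108 events, HR 0.25), 13% (108 events, HR 0.5, which the plan does not assume) and 11% (40 events, HR 0.25).

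**5. Long against short list.** Assumptions: 800 trials per cell, N = 2000, 25% F4, non-SVR12 3.5% in F0-F3 and 5.5% in F4, cirrhosis HR 3; platelets, albumin and AFP each HR 1.4 per SD; platelets and albumin also OR 1.22 per SD for non-SVR12; true SVR12 HR 0.25. Component counts of 40, 20 and 10 are assumptions, as the documents give none. The short model has SVR12, platelets and albumin, stratified by F4 and study. SD of the SVR12 log HR:

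| Events | Full, 27 / 35 parameters | Short |
|---|---|---|
| 108 | 0.31 / 0.31 | 0.28 |
| 40 | 0.53 / 0.56 | 0.50 |
| 20 | 0.74 / 0.81 | 0.66 |
| 10 | 1.15 / 1.59 | 0.70 |

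Coverage was 92-94% (full) and 95-97% (short). At 10 events the average HR among finite fits was 0.16 / 0.13 (full) and 0.22 (short). Repeating that cell gave SD 1.15 against 0.64 and average HR 0.16 against 0.23. No usable SVR12 estimate arose in 19% / 20% (full) and 18% (short) of trials; non-SVR12 had zero events in 18%. Firth's penalty on the short model gave an estimate every time, with average HR 0.24 and coverage 97%.

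**6. Unadjusted log-rank, no true SVR12 effect.** Non-cirrhotic failure is 38/1475 = 2.6% (studies in Protocol 3.0 without cirrhosis, leaving out the ribavirin-free GT1a arm). Cirrhotic failure in M13-099 was 4.1% (24 weeks) and 8.2% (12 weeks). The rate implied by this plan's assignment rules comes from Protocol Table 1 weighted by the M13-099 mix, taking subtype and treatment history as independent:

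- Current default (GT1a 24 weeks, GT1b 12 weeks): 0.687 × (0.421 × 7.1 + 0.361 × 7.1) + 0.313 × (0.082 × 14.3) = 4.2%.
- Earlier rule (24 weeks only for GT1a null responders or nonresponders): 5.0%.
- Twelve weeks for all: 8.1%.

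With cirrhosis HR 2 to 5 (assumed), the log-rank test rejects in about 6-9% of trials at 4.1%, 7-12% at 5.0% and 10-23% at 8.2%. Stratified by F4 it rejects in about 5%. If overall failure is instead held at 4%, a cirrhotic rate of 4.1% is hardly different from the rest and the unstratified test also stays near 5%.

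**The case against.** The strongest defence is that a broad covariate list is a reasonable guard against confounding in a non-randomised comparison, and that cirrhosis is already in the Cox model through fibrosis stage, Child-Pugh, FibroTest, platelets and albumin. Unadjusted Kaplan-Meier and log-rank results beside an adjusted Cox model are common practice. This stands for the composite. The simulation gave a confounding role only to cirrhosis, platelets and albumin, which the short model keeps, so it cannot show that the omitted characteristics are harmless.

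It is also fair that the trouble at 10 events is partly a limit of the data: the short maximum-likelihood model failed almost as often as the full one, because non-SVR12 subjects had no events. List length still matters there, since the SD and the bias were clearly worse with the full list.

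A reader might infer more than the documents support:

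- That the composite result would be invalid. Coverage is near nominal and the loss of precision is small.
- That the power statement is wrong. It is reproduced.
- That missing covariates have no rule. SAP 6.3 implies complete-case; what is absent is a rule for the Cox models that limits the loss.
- That the log-rank test is badly inflated. The 10-23% range needs a cirrhotic failure rate of 8.2%, which the 24-week default for GT1a cirrhosis largely avoids.

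**Conclusion.** The point holds, at moderate size. For the composite, the SVR12 hazard ratio can be estimated with little bias (SD of log HR about 0.30 against 0.28); the real weakness is that its value depends on codings the SAP has not fixed. For rare components, following SAP 10.3 as written gives an unstable estimate that exaggerates the SVR12 effect, and a shorter list alone would not cure it. The unadjusted log-rank test is mildly liberal under the failure rates that the plan's own treatment rules imply. The Year-5 test is unadjusted in the same way.

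These sizes rest on assumed component counts, covariate distributions and cirrhosis hazard ratios. The share of subjects without AFP is not stated, so that loss cannot be sized. The parameter range is a count from SAP 7.1 and would rise if the demographics were included.

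**What to change.** Before the final database lock, amend SAP 10.3:

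1. Stratify the log-rank test by F4 against F0-F3, and label the Year-5 Kaplan-Meier test as unadjusted.
2. Fix one coding per Cox covariate and drop redundant forms, including the Child-Pugh non-cirrhotic level that duplicates fibrosis stage.
3. State an event count below which a component is analysed with SVR12 and F4 strata, plus at most a few named covariates, by penalised likelihood (for example Firth) with profile intervals.
4. Leave AFP out of the main model, or state a method that keeps subjects without it.

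For the composite, the sponsor may choose a short or a broad list as the main model, named in advance, with the other reported as sensitivity.

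The cost is SAP wording and programming; no new visits or data are needed. The downside is possible residual confounding in the reduced component models. As a guide, at 108 events SVR12 with strata alone gave an average HR of 0.23 for a true 0.25 (coverage 93%) when platelets and albumin also predicted SVR12 failure.

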10.4 Secondary Efficacy Analyses

The following analyses of secondary efficacy endpoints will be performed on the ITT-I population:

- The effect of sustained virologic response on change and percentage change from baseline in FibroScan score (assessed at the end of treatment and all post-treatment visits except PT Week 4) will be evaluated by comparing mean change from baseline at each applicable visit between subjects who achieve SVR₁₂ and those who do not using descriptive statistics and ANCOVA analyses. SVR₁₂ status will be included as a factor and baseline FibroScan score will be included as a covariate in the ANCOVA model. From the ANCOVA analyses, point estimates of the mean difference and 95% confidence intervals will be provided.
- Sustained virologic response will be evaluated using the percentage of subjects achieving SVR₁₂ (HCV RNA < LLOQ 12 weeks after the last actual dose of study drug). The simple percentage of subjects achieving SVR₁₂ will be calculated and a two-sided 95% confidence interval of the percentage will be computed based on Wilson's score method.

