#### **8.1.2.2 Secondary Efficacy Endpoints**

The secondary efficacy endpoints are:

- The effect of sustained virologic response and baseline fibrosis stage on longitudinal change from baseline in Fibroscan score (assessed at the end of treatment and/or post-treatment visits) will be evaluated by comparing mean change between subjects who achieve SVR12 and those who do not. Point estimates and 95% confidence intervals will be provided.
- The percentage of subjects achieving SVR12 (HCV RNA < LLOQ 12 weeks after the last actual dose of study drug). The simple percentage of subjects achieving SVR12 will be calculated and a two-sided 95% confidence interval of the percentage will be computed based on Wilson's score method.

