4.3 Sample Size

Assuming 4% of subjects do not achieve SVR₁₂ and assuming the 5-year event rate of the composite clinical outcome is 20% in the non-SVR₁₂ subjects, with a 75% reduction in SVR₁₂ subjects (Hazard Ratio of 0.25),^{1,2} then based on two-sample log rank test (using EAST 6.0), a sample size of at least 2000 subjects enrolled in TOPAZ-I (planned to enroll 1650 subjects) and TOPAZ II (planned to enroll 600 subjects) provides greater than 80%

power to reject the null hypothesis of no difference between SVR₁₂ and non-SVR₁₂ subjects in the rate of clinical outcome events. Power calculations were based on a dropout rate of up to 20% for the hazard ratio.

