4.4 Planned Analysis

The primary analysis to evaluate the effect of response to treatment on clinical outcomes, will occur at the final analysis after all subjects have completed the study or prematurely discontinued the study. An interim analysis to assess the percentage of subjects achieving SVR₁₂ will occur after all subjects have completed the Post-Treatment Week 12 Visit or prematurely discontinued the study. For both final and interim analyses, data will be locked after performing appropriate data cleaning. Data after the interim analysis will be added to a subsequent version of the database. SAS[®] (SAS Institute, Inc., Cary, NC) for the UNIX operating system will be used for all analyses. All statistical tests and all confidence intervals will be two-sided with an α level of 0.05.

All analyses will be conducted by statisticians and statistical programmers at AbbVie or the designee according to the methodologies specified in this SAP.

There is no intention of shortening the follow-up time of subjects based on efficacy findings from the interim analysis. The intention is to follow all subjects who receive study drug for 260 weeks following treatment. There will be no statistical adjustment employed due to this interim analysis.

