6.3 Missing Data Imputation

No data will be imputed for any efficacy or safety analyses except for the PRO questionnaires, for analyses of the HCV RNA endpoints, and for analysis of the persistence of resistance. If a respondent answers at least 50% of the items in a multi-item scale of the SF-36v2, the missing items will be imputed with the average score of the answered items in the same scale. In cases where the respondent did not answer at least 50% of the items, the score for that domain will be considered missing. Similarly, the missing items of the FACIT-F questionnaire will be imputed with the average score of the answered items in the same scale as long as more than 50% (≥ 7 out of 13) of the items in the scale are answered. The SF-36v2 Mental and Physical Component Summary measures will not be computed if any domain is missing.

HCV RNA values will be selected for an SVR analysis based on visit windows as defined in Section 6.2. When there is no HCV RNA value in a visit window based on defined visit windows, the closest values before and after the window, regardless of the value chosen for the subsequent and preceding window, will be used for the flanking imputation described below.

If a subject has a missing HCV RNA value at a post-Day 1 visit but with undetectable or unquantifiable HCV RNA levels at both the preceding value and succeeding value, the HCV RNA level will be considered undetectable or unquantifiable, respectively, at this visit for this subject. In addition, if a subject has an unquantifiable HCV RNA level at the preceding value and an undetectable HCV RNA level at the succeeding value, or vice versa, the HCV RNA level will be imputed as unquantifiable at this visit for this subject. For SVR analyses, if there is no value in the appropriate window after flanking imputation but there is an HCV RNA value after the window, then it will be imputed into the SVR window. Subsequent to this flanking and backward imputation, if a subject is missing a value for the visit window associated with the analysis, the subject will be imputed as a visit failure (i.e., not undetectable or unquantifiable).

If a subject starts another treatment for HCV, then all HCV RNA and PRO assessment values for this subject measured on or after the start date of the new HCV treatment will be excluded from analyses. The subject will be considered a failure for summaries of viral response at all time points after the start of the new HCV treatment.

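### SAP 10.4 analyses five years of FibroScan by separate observed-case ANCOVAs; if stiffness-related dropout differs by SVR12 status, the late SVR12 difference is modestly biased toward zero, and one repeated-measures model would correct most of this

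*SAP*

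**What the plan says.** Protocol 8.1.2.2 describes the endpoint as the effect of sustained response and baseline fibrosis stage "on longitudinal change from baseline in Fibroscan score (assessed at the end of treatment and/or post-treatment visits"). The same sentence then calls for a comparison of mean change by SVR12 status, with point estimates and 95% confidence intervals. Protocol 5.3.2.2 defines the variable as mean change from baseline in FibroScan score, when available.

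SAP 10.4 implements this visit by visit: the effect "will be evaluated by comparing mean change from baseline at each applicable visit between subjects who achieve" SVR12 and those who do not. The ANCOVA has SVR12 status as factor and baseline FibroScan as covariate. The visits are end of treatment and PT Weeks 12, 24, 52, 104, 156, 208 and 260, eight in all. SAP 10.5 says outright that the subgroup models are fitted separately by visit.

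On missing data, SAP 6.3 states "No data will be imputed for any efficacy or safety analyses except for the PRO questionnaires", HCV RNA endpoints and persistence of resistance. FibroScan is not among the exceptions. The sensitivity analyses in SAP 10.6 concern SVR12 only. Under Protocol 5.4.1, a subject who leaves the study is contacted for survival status only, so no later scan exists.

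**The concern.** A per-visit model at PT Week 260 uses only those scanned at that visit. It adjusts for baseline stiffness but not for what happened between end of treatment and year 4, although those scans are in the database. If non-SVR12 subjects whose stiffness rises are more likely to stop being scanned, the late non-SVR12 mean comes from a healthier remainder and the SVR12 difference is understated.

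Such a pattern is plausible from the documents, though nowhere quantified. Protocol 3.0 places the greatest complication risk in advanced fibrosis. SAP 4.3 expects four times the hazard of serious outcomes without SVR12. Protocol 5.3.1.1 lets outcome information be taken by telephone when a subject cannot attend, which yields no scan.

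At stake is the late estimate of a secondary endpoint, in a comparison whose smaller group has about 66 subjects at most.

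**Working it through.** **1. The plan's own figure.** The only power statement concerns the composite clinical outcome; none is given for FibroScan. Inputs from SAP 4.3: "Assuming 4% of subjects do not achieve" SVR12; "the 5-year event rate of the composite clinical outcome is 20% in the non-SVR"12 subjects; "Hazard Ratio of 0.25"; "a sample size of at least 2000 subjects enrolled in TOPAZ-I (planned to enroll 1650 subjects") and TOPAZ-II; dropout up to 20%. From SAP 4.4: "All statistical tests and all confidence intervals will be two-sided with an α level of 0.05".

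- Event hazard without SVR12: −ln(0.80)/5 = 0.0446 per year. With SVR12: 0.25 × 0.0446 = 0.0112. Dropout hazard: −ln(0.80)/5 = 0.0446.
- Event probability without SVR12: 0.0446/0.0892 × (1 − 0.64) = 0.18. With SVR12: 0.0112/0.0558 × (1 − 0.757) = 0.0487.
- Events: 80 × 0.18 + 1920 × 0.0487 = 14.4 + 93.5 = 107.9.
- Schoenfeld power: Φ(√(107.9 × 0.04 × 0.96) × ln 4 − 1.96) = Φ(0.86) = 80.6%.

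The stated figure of more than 80% reproduces. The planning allowance for dropout is not split by SVR12 status or by stiffness.

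**2. Group sizes for FibroScan.** Non-SVR12 in this study: 4% × 1650 = 66; SVR12: 1584. FibroScan is done only where available (Protocol Table 7, note s) and the share of sites is not given. Assuming 50% to 100%, the non-SVR12 group is 33 to 66.

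**3. When the per-visit ANCOVA is biased.** For group g, let s(g) be the mean PT Week 260 stiffness of those still scanned minus that of everyone in the group, given baseline. The bias in the ANCOVA difference is the difference between the two s(g).

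- Dropout random or dependent on baseline only: both s(g) are 0, so there is no bias.
- Dropout dependent on earlier stiffness with equal rates and slopes: the two s(g) cancel.
- Rate or slope differing by group, or a common rule with a stiffer non-SVR12 group: they do not cancel. If stiffer non-SVR12 subjects leave more, the bias is toward zero.

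**4. Size in kPa (all inputs assumed).** True difference at PT Week 260 is 3.0 kPa, SD 6 kPa and adjacent-visit correlation 0.8, with monotone dropout. The log-odds of dropping out rise by b per SD of the last observed change; b = 0.5 gives 1.65-fold and b = 1.0 gives 2.7-fold odds. The repeated-measures estimate is maximum likelihood with unstructured covariance. With monotone missingness it is obtained exactly by regressing each visit on group, baseline and earlier visits.

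| Dropout mechanism | ANCOVA (kPa) | Shortfall from 3.0 | Repeated measures (kPa) |
|---|---|---|---|
| One rule in both groups, about 20% | 2.85-3.0 | 0-5% | about 3.0 |
| Non-SVR12 only, 20% dropout, 1.65-fold | 2.7 | 10% | about 3.0 |
| Non-SVR12 only, 20% dropout, 2.7-fold | 2.5 | 17% | about 3.0 |
| Non-SVR12 only, about a third lost, 2.7-fold | 2.2 | 27% | about 3.0 |

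**5. Second simulation, in SD units.** True difference 0.50 SD, 1584 and 66 subjects, dropout from PT Week 52, 1500 runs per case.

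- Random dropout, baseline-only dropout, or equal rates and slopes: bias about 0.00 for both methods.
- One identical rule at 20% overall: ANCOVA 0-9% toward zero; repeated measures within 0.006 SD of the truth.
- Dropout 20% (SVR12) and 40% (non-SVR12), slope 1: ANCOVA 0.45, repeated measures 0.50. With 20% and 60%: 0.39 and 0.50.
- Dropout driven by the current, unseen value (20% and 40%): bias 0.06 for ANCOVA and 0.03 for repeated measures.

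**6. Against noise.** In the kPa setting with 33 non-SVR12 subjects and random dropout, the standard error is 1.15 for ANCOVA and 1.09 for repeated measures, a gain of 1 − 1.09/1.15 = 5%. In SD units with 66 it is 0.100 and 0.098, a gain of 2%. At n = 33, shortfalls of 0.3, 0.5 and 0.8 kPa are 0.26, 0.43 and 0.70 standard errors. At n = 66, taking 1.15/√2 = 0.81, they are 0.37, 0.62 and 0.98.

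**The case against.** The strongest reply is that the plan does what the protocol asks, for an unpowered secondary estimate gathered only where the device exists, and that the bias is small against noise and needs a mechanism nobody has measured. Much of that stands. Protocol 3.0 even reports delayed fibrosis progression in relapsers and falling stiffness after interferon-based treatment, so steep worsening in the non-SVR12 group cannot be taken for granted.

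Four stronger readings should be resisted.

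- A reader might infer that the per-visit ANCOVA is valid only if being scanned at year 5 is unrelated to stiffness at years 1 to 4. That is too strict: equal dependence in both groups cancels in the difference.
- A reader might expect about a third of the effect to be lost at the planned 20% dropout. Averages of 1.8-2.2 kPa at 2.7-fold arise only when 20% describes the SVR12 group and the non-SVR12 group loses about 27-38%.
- A reader might take the word longitudinal in Protocol 8.1.2.2 as a requirement that the SAP breaches. The rest of that sentence asks for a comparison of mean change, which SAP 10.4 delivers.
- A reader might expect a repeated-measures model to recover the truth whatever the cause of dropout. It removed only about half the bias when dropout followed the unseen value. After death it also estimates stiffness as if the subject could still be scanned.

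What remains is that earlier scans already collected go unused where they would help, and that no missing-data sensitivity analysis is planned for this endpoint.

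**Conclusion.** The point holds as a modest, conditional weakness in a secondary analysis. The late SVR12 difference in FibroScan is biased toward zero if missing scans depend on post-baseline stiffness beyond baseline and more so, in rate or slope, in the non-SVR12 group. A common rule combined with a stiffer non-SVR12 group also suffices.

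Under the assumptions shown, the loss is 0-5% of a 3.0 kPa difference under one common rule at about 20% dropout. It is 10-17% when the relation is confined to a non-SVR12 group with 20% dropout, and about 27% when that group loses about a third. This is usually less than one standard error, and the precision gain from repeated measures is about 1-5%.

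The documents give no FibroScan SD, visit correlation, site share or relation between stiffness and dropout, so the size is illustrative; the direction rests on stiffer non-SVR12 subjects leaving more often. The primary time-to-event analysis is not affected. The change is worth making because it is cheap and, in the cases run, the repeated-measures model was never materially more biased than the ANCOVA.

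**What to change.** In SAP 10.4, estimate the SVR12 difference at each visit from one mixed model for repeated measures. Terms: SVR12, visit, SVR12-by-visit, baseline FibroScan and baseline-by-visit, with unstructured covariance and a named fallback structure if the model does not converge. Keep the per-visit means as descriptive output and the per-visit ANCOVA as a sensitivity analysis.

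Add two statements. First, the model corrects only for dropout that depends on observed values. Second, say how the analysis treats scans missing after death or transplantation, and scans taken after new HCV treatment. SAP 6.3 excludes HCV RNA and PRO values after new treatment but does not mention FibroScan.

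The cost is a paragraph of SAP text, one additional model on data already being collected, and the choice of a covariance structure. No visit, procedure or sample size changes.
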